**Table 3: Procedures and Assessments in Part B of IM011073 (52-Week Blinded Treatment Period)**

Visit Number	B1	B2	B3	B4	B5	B6	B7	B8	B9	B10	B11	B12	B13	B14/ EOT a	B15 a	Notes
Study Week/Day	D1	W4 D29 ±3d	W8 D57 ±3d	W12 D85 ±3d	W16 D113 ±3d	W20 D141 ±3d	W24 D169 ±3d	W28 D197 ±3d	W32 D225 ±3d	W36 D253 ±3d	W40 D281 ±3d	W44 D309 ±3d	W48 D337 ±3d	W52 D365 ±3d	28-D FU ±3d	The final study visit (for noncontinuing subjects) will occur 28d±3d after the visit at W52
Confirm study eligibility criteria are still met	X															
Evaluate for randomization	X															
Body weight & vital signs	X	X	X	X	X	X	X	X	X	X	X	X	X	X	X	BP and HR should be measured after the subject has been sitting quietly for at least 5 minutes
Complete physical examination	X	X	X	X	X	X	X	X	X	X	X	X	X	X	X	
Concomitant medications	X	X	X	X	X	X	X	X	X	X	X	X	X	X	X	
12-lead ECG	X	X	X				X						X	X		
AEs and SAEs	X	X	X	X	X	X	X	X	X	X	X	X	X	X	X	Section 8.5
Subject Status Evaluation							X									Section 7.2
Indices of disease activity and damageb																
rSFI		X	X	X	X	X	X	X	X	X	X	X	X	X	X	All systems except renal; clinical component only (not treatment) APPENDIX 17
OSS Flare Index		X	X	X	X	X	X	X	X	X	X	X	X	X	X	APPENDIX 16

**Table 3: Procedures and Assessments in Part B of IM011073 (52-Week Blinded Treatment Period)**

[figure not shown]
Visit Number	B1	B2	B3	B4	B5	B6	B7	B8	B9	B10	B11	B12	B13	B14/ EOT a	B15 a	Notes
Study Week/Day	D1	W4 D29 ±3d	W8 D57 ±3d	W12 D85 ±3d	W16 D113 ±3d	W20 D141 ±3d	W24 D169 ±3d	W28 D197 ±3d	W32 D225 ±3d	W36 D253 ±3d	W40 D281 ±3d	W44 D309 ±3d	W48 D337 ±3d	W52 D365 ±3d	28-D FU ±3d	The final study visit (for noncontinuing subjects) will occur 28d±3d after the visit at W52
Laboratory tests and other procedures																
UA with microscopic examination		X	X	X	X	X	X	X	X	X	X	X	X	X	X	Clean-catch specimen; if the UA is positive for leukocytes, blood, or bacteria, a urine culture should be performed if appropriate
UPCR		X	X	X	X	X	X	X	X	X	X	X	X	X		First morning voided specimen; second morning void may be used if first morning void was not collected
24-hour urine for UPCR c							X and ±7d							X and ±7d		Two 24-hour urine specimens will be collected for Visits B7 and B14; one should be collected at the visit and one returned either before or after per site/subject preference. The subject must provide both samples within the total 14-day window.
Urine pregnancy test for WOCBP only	X	X	X	X	X	X	X	X	X	X	X	X	X	X	X	A negative result within 24 hours before dosing on D1 is required

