**Table 3: Procedures and Assessments in Part B of IM011073 (52-Week Blinded Treatment Period)**

[figure not shown]
Visit Number	B1	B2	B3	B4	B5	B6	B7	B8	B9	B10	B11	B12	B13	B14/ EOT a	B15 a	Notes
Study Week/Day	D1	W4 D29 ±3d	W8 D57 ±3d	W12 D85 ±3d	W16 D113 ±3d	W20 D141 ±3d	W24 D169 ±3d	W28 D197 ±3d	W32 D225 ±3d	W36 D253 ±3d	W40 D281 ±3d	W44 D309 ±3d	W48 D337 ±3d	W52 D365 ±3d	28-D FU ±3d	The final study visit (for noncontinuing subjects) will occur 28d±3d after the visit at W52
MMF accountability	X	X	X	X	X	X	X	X	X	X	X	X	X	X	X	All subjects
Blinded study treatment issued	X	X	X	X	X	X	X	X	X	X	X	X	X	X d		Randomized subjects only
Blinded study treatment administration	X-----X														Randomized subjects only	
Blinded study treatment accountability		X	X	X	X	X	X	X	X	X	X	X	X	X		Randomized subjects only
Unused blinded study treatment collected		X	X	X	X	X	X	X	X	X	X	X	X	X		Randomized subjects only

aCl = anticardiolipin antibody; AE = adverse event; ANA = antinuclear antibody; APA = antiphospholipid antibody; β2GPI = beta-2 glycoprotein 1; BP = blood pressure; C = complement; D = day; ECG = electrocardiogram; EOT = end of treatment; ET = early termination; FU = follow-up (end-of-study visit); HR = heart rate; hsCRP = high-sensitivity C-reactive protein; Ig = immunoglobulin; IGRA = interferon-gamma release assay; IP = investigational product; IRT = interactive response technology; LA = lupus anticoagulant; MPA = mycophenolate mofetil; MPA = mycophenolic acid; OSS = Ohio SLE Study; rSEI = revised Safety of Estrogens in Lupus Erythematosus National Assessment (SELENA) Flare Index; SAE = serious adverse event; TB = tuberculosis; UA = urinalysis; UPCR = urine protein:creatinine ratio; US = United States; W = week; WOCBP = women of childbearing potential

a Visit B14 is the last treatment visit for subjects who do not continue treatment during the LTE Period. Only these noncontinuing subjects should attend Visit B15.  
b Subjects should be instructed to not take pain medication for 12 hours before all study visits in Part B except for the 28-day follow-up visit (Visit B15).  
c If the difference in UPCR values between the two 24-hour urine collections for Visits B7 and B14 is > 20%, a third 24-hour urine will be collected to determine the average; this third sample should be collected as soon as possible but no more than 10 days after the first two results are reported.  

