d Only subjects continuing to the LTE Period will be issued MMF and blinded study treatment at the Week 52 visit for Week 52 through Week 56.  
 Note: Unless they withdraw consent for follow-up, randomized subjects who discontinue the IP early will remain in the study for follow-up purposes including Visit B15; these subjects will be assessed on a case-by-case basis regarding the optional end-of-study renal biopsy.  
 Note: For premenopausal women, study visits and 24-hour urine collections should be scheduled, when possible, for when they are not menstruating.

[figure not shown]

[figure not shown]

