## **7.2 Week 24 Subject Status Evaluation**

At Week 24 (Visit B7), investigators should assess, based on their clinical judgment, if continuation in the study remains in the subject's best interest, overall and with regard to progression of renal disease. If the investigator determines that continuation is no longer in a subject's best interest, the subject should stop the study treatment immediately, but if possible, should remain in the study for appropriate follow-up procedures as outlined in Sections 7.3 and 7.4. The investigator will record the reason for discontinuation and will report any AEs or SAEs (see [Section 8.5](#) and [APPENDIX 3](#)).

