### 8.4.1 Efficacy Assessments

[figure not shown]
The following assessments will be done during the study (see [Section 1.3](#)):

- Laboratory assessments:
  - [REDACTED]
  - Urinalysis with microscopic examination (clean-catch specimen); if the urinalysis is positive for leukocytes, blood, or bacteria, a urine culture should be performed if appropriate
  - UPCr based on the first morning voided urine specimen (if the first morning voided specimen was not collected, the second morning void will be used)
  - UPCr based on 24-hour urine collections:
    - Two 24-hour urine specimens will be collected for Visits A4 (baseline), B7, and B14 (except for subjects with  $\geq 12$  weeks of MMF at a dose of 1.5 to 3.0 g/day at the time of screening, who will collect a single 24-hour urine to be compared to their 24-hour UPCr at screening); if the difference in UPCr values between specimens is  $> 20\%$ , a third 24-hour urine specimen will be collected as soon as possible but no more than 10 days after the results of the results of the first two samples are reported
      - If the third value is within 20% of only one of the previous 2 values, the 2 closest values will be used to compute the average UPCr
      - If the third value is within 20% of both previous values (in the middle), then all 3 values will be used to compute the average UPCr

- If the third value is not within 20% of either of the previous values (all 3 values are > 20% different from each other), then all 3 values will be used to compute the average UPCR
  - [REDACTED]
  - High-sensitivity C-reactive protein (hsCRP)
  - Antiphospholipid antibodies (APAs): anticardiolipin antibody (aCL), lupus anticoagulant (LA), and anti-beta-2 glycoprotein-1 (β2GP1) (immunoglobulin [IgA], IgG, and IgM)
  - [REDACTED]
  - Antinuclear antibody (ANA)
  - [REDACTED]
- Disease activity and damage indices:
  - [REDACTED]
  - SLICC/ACR SDI see [APPENDIX 10](#)
  - rSFI – clinical component only (excluding the renal system, which is assessed with the OSS Flare Index) see [APPENDIX 17](#)
  - OSS Flare Index; see [APPENDIX 16](#)

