### 9.5.1 Adverse Events

Treatment-emergent AEs, AEs, SAEs, deaths, AEs leading to discontinuation of IP, AEs by maximum severity, and AEs by relationship to IP will be summarized by the Medical Dictionary for Regulatory Activities system organ class and preferred term by (1) treatment arm in Part B and (2) in LTE period for the following 4 treatment groups separately:

- Group 1: BMS-986165 3 mg BID → BMS-986165 3 mg BID
- Group 2: BMS-986165 6 mg BID → BMS-986165 6 mg BID
- Group 3: Placebo BID → BMS-986165 3 mg BID
- Group 4: Placebo BID → BMS-986165 6 mg BID

AEs for combined BMS-986165 3 mg BID (Group 1 and Group 3) and BMS-986165 6 mg BID (Group 2 and Group 4) may also be summarized as described in the SAP.

All TEAEs, AEs, as well as any potential adjudicated AE category will also be summarized by preferred term sorted by decreasing frequency.

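### The Week 52 24-hour UPCR can include urine passed after Part B treatment has ended or changed, and no visible rule excludes it.

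*Combined protocol and SAP*

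**What the plan says.** Table 3 (Section 1.3) schedules the 24-hour urine for UPCR at B7 (Week 24) and B14 (Week 52) with a margin of 7 days either side. Two specimens are needed: "one should be collected at the visit and one returned either before or after per site/subject preference". The same note adds: "The subject must provide both samples within the total 14-day window".

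Footnote c covers pairs that differ by more than 20%: "this third sample should be collected as soon as possible but no more than 10 days after the first two results are reported". Section 8.4.1 gives the averaging rule. If the third value agrees with only one of the first two, "the 2 closest values will be used to compute the average"; otherwise all three are averaged.

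Footnote a says: "Visit B14 is the last treatment visit for subjects who do not continue treatment during the LTE Period". Under footnote d, continuing subjects "will be issued MMF and blinded study treatment at the Week 52 visit for Week 52 through Week 56". Section 9.5.1 lists the extension groups for the safety summaries, including "Group 3: Placebo BID → BMS-986165 3 mg BID" and a matching group that goes from placebo to 6 mg BID.

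The note to the Section 3 table says that 24-hour specimens supply the UPCR at baseline, Week 24 and Week 52. Section 9.3.3 builds CRR, PRR and CRR with steroid taper at Week 52 on that value. The set-to-missing rule in Section 9.4.2.1 concerns prohibited medication or therapy that could improve lupus nephritis.

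**The concern.** A Week 52 response should describe the subject on the treatment assigned for Part B. Table 3 lets part of the measurement come from a later period. In that period a subject who is not continuing has finished blinded treatment, and a continuing placebo subject may already be taking active drug.

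Both changes would be expected to narrow the difference between arms. Placebo subjects gain drug, and active subjects who decline the extension lose it. Whether the second specimen falls before or after the visit is left to preference, so exposure to the problem varies by site and subject.

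At stake are three Week 52 secondary endpoints. All are binary with fixed cut-offs, and the placebo arm has 26 subjects.

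**Working it through.** **1. Collection windows.** Plus or minus 7 days gives 7 + 7 = 14 days, which matches the plan's stated total. B14 is Day 365 ± 3, so the second specimen can be as late as Day 365 + 3 + 7 = 375, which is 7 days after the visit.

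A third specimen cannot be called for until both results are reported, and one of those two is collected at the visit. It therefore always falls after B14. With laboratory turnaround of L days (not stated), the latest third specimen is:
- second specimen before the visit: 10 + L days after B14
- second specimen 7 days after the visit: 7 + L + 10 = 17 + L days after B14

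For an assumed L of 0 to 7 days this is 10 to 17 days and 17 to 24 days. All of these fall within the Week 52 to 56 period that the extension supply covers.

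**2. Treatment state in those days.**

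| Subject | State after B14 | Basis |
|---|---|---|
| Not continuing, any arm | Blinded treatment finished | Table 3, footnotes a and d |
| Continuing, active | Stays on the same dose | Section 9.5.1, Groups 1 and 2 |
| Continuing, placebo | Moves to 3 mg or 6 mg BID; start with the B14 supply is inferred | Footnote d with Section 9.5.1, Groups 3 and 4 |

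The prohibited-medication rule in Section 9.4.2.1 covers neither change.

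**3. How often a third specimen arises.** The documents give no within-subject variability, so the CV is assumed. With lognormal error, s = √ln(1 + CV²). Taking the difference relative to the pair mean, it exceeds 20% when the log difference exceeds 2·atanh(0.1) = 0.2007. The probability is 2·[1 − Φ(0.2007 / (s√2))].

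| CV | s | Probability |
|---|---|---|
| 10% | 0.0998 | 0.15 |
| 15% | 0.149 | 0.34 |
| 20% | 0.198 | 0.47 |
| 30% | 0.294 | 0.63 |

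The plan does not say what the 20% is relative to. At CV 20%, using the larger value gives 0.43 and using the smaller gives 0.51.

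**4. Weight on post-visit urine.** The Section 8.4.1 averaging rule was simulated at CV 20% with 1,000,000 draws and no true change over time. The mean weight on post-visit specimens is 21% if every second specimen is taken before the visit and 61% if every one is taken after. If half are taken after, it is (21 + 61)/2 = 41%. Among subjects who choose after, about 16% have a value resting on post-visit urine alone, because the two closest values are the second and third specimens. Moving only the second specimen therefore leaves the third-specimen share in place.

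**5. What a shift does at the cut-off.** Suppose urine passed after the switch is lower by a fraction f (assumed 5% to 20%). With one specimen before and one after the switch, the average falls by f/2, or 2.5% to 10%. A placebo subject then meets the CRR limit of 0.5 mg/mg with an on-treatment UPCR up to 0.5/(1 − f/2):
- f = 5%: 0.513
- f = 10%: 0.526
- f = 20%: 0.556

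If both averaged specimens follow the switch, the limit is 0.5/(1 − f), or 0.526 to 0.625. The same ratios apply to PRR: an on-treatment reduction of 48.7% (f = 5%) or 44.4% (f = 20%) would count as 50%.

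Each reclassified subject moves the placebo rate by 1/26 = 3.8 points, or the combined active rate by 1/52 = 1.9 points. How many subjects lie in these bands is unknown.

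**The case against.** **Redaction.** Footnote d says when extension drug is issued, not whether the first dose waits for outstanding urines. Section 9.5.1 defines safety-summary groups, and Section 9.4 leaves analysis detail to the SAP. A safeguard may exist in text that is not visible. This stands as a caveat on the placebo switch. It does not touch subjects who end treatment at B14, which is stated openly.

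**Week 24.** A reader might infer that the primary endpoint is compromised too, because the same timing note covers B7. The documents do not support that. No switch is scheduled at B7. Section 6.6.1 asks for a stable steroid dose until the Week 24 efficacy assessments, and the 24-hour urine is naturally read as one of those. Section 7.2 can end treatment at that visit ("the subject should stop the study treatment immediately"), but only case by case on clinical judgment. Excluding urine after such a decision would make the primary value depend on a post-randomization choice.

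**Size.** A reader might also want a percentage loss of treatment effect. That would need the speed of onset, the share choosing after and the within-subject CV, none of which the documents give. It would also describe a continuous contrast, whereas the visible Week 52 efficacy endpoints are binary.

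**Who is affected.** Section 9.4.2.1 already counts early discontinuers as nonresponders, so loss of drug matters only for subjects who complete Week 52 and decline the extension. The eGFR part of CRR uses chemistry scheduled at the visit, so only the UPCR part is exposed.

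**Precedent.** Visit A4 is not an exact model for the fix. Its routine specimens precede the visit, but subjects with at least 12 weeks of MMF use the screening urine as the first one, and a third specimen after A4 is allowed.

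**Conclusion.** The point holds for Week 52. Followed as written, the plan lets the UPCR behind CRR, PRR and CRR-plus-taper include urine passed after Part B treatment has ended, or probably after placebo subjects have started active drug. No visible rule removes it.

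The expected direction is toward no difference. The size cannot be established: the third-specimen rates and the cut-off examples rest on assumed CVs and assumed changes in UPCR, and they show the mechanism rather than an estimate of bias. Urine within 7 days of B14 may differ little; a third specimen two to three weeks later has more room to.

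The affected endpoints are secondary, tested with nominal p-values, and the Week 24 primary endpoint is not materially affected. This is an inexpensive improvement to make, not a flaw that undermines the trial.

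**What to change.** In Table 3 and Section 8.4.1, require both routine B14 24-hour specimens in the 7 days up to and including the visit and before the first extension dose.

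In the analysis plan, base the main Week 52 UPCR on specimens collected within the Part B treatment period or before the first extension dose. Report a sensitivity analysis that adds later third specimens under the existing averaging rule. Record the collection dates of each specimen and the dates of the last Part B dose and the first extension dose, so that the rule can be applied. Week 24 needs no exclusion rule. If redacted text already contains such a safeguard, a cross-reference is enough.

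The cost is a collection window of 7 days instead of 14. That leaves less room for the advice to avoid menstruation when scheduling. Discordant Week 52 pairs would also often rest on two specimens in the main analysis. At assumed CVs of 15% to 30%, that could concern roughly 34% to 63% of Week 52 pairs, so the sensitivity analysis should be kept. No dose, visit or sample size changes.

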**Table 3: Procedures and Assessments in Part B of IM011073 (52-Week Blinded Treatment Period)**

Visit Number	B1	B2	B3	B4	B5	B6	B7	B8	B9	B10	B11	B12	B13	B14/ EOT a	B15 a	Notes
Study Week/Day	D1	W4 D29 ±3d	W8 D57 ±3d	W12 D85 ±3d	W16 D113 ±3d	W20 D141 ±3d	W24 D169 ±3d	W28 D197 ±3d	W32 D225 ±3d	W36 D253 ±3d	W40 D281 ±3d	W44 D309 ±3d	W48 D337 ±3d	W52 D365 ±3d	28-D FU ±3d	The final study visit (for noncontinuing subjects) will occur 28d±3d after the visit at W52
TB questionnaire and IGRA assay							X						X			Only subjects who have indeterminate test results for TB must fill out the TB questionnaire and have a repeat IGRA test. Refer to Section 8.7.2 and APPENDIX 20 .
Routine chemistry and hematology		X	X	X	X	X	X	X	X	X	X	X	X	X	X	Section 8.7.3.2
Trough MPA concentration							X							X		Subjects should not have taken MMF for at least 10 hours before sample is collected
Serum lipid panel							X							X		Subjects are required to fast at least 10 hours before sample is collected
hsCRP		X	X	X	X	X	X	X	X	X	X	X	X	X		
ANA							X							X		
APAs							X							X		LA, aCl, and anti-β2GP1 (IgA, IgG, IgM)

**Table 3: Procedures and Assessments in Part B of IM011073 (52-Week Blinded Treatment Period)**

Visit Number	B1	B2	B3	B4	B5	B6	B7	B8	B9	B10	B11	B12	B13	B14/ EOT a	B15 a	Notes
Study Week/Day	D1	W4 D29 ±3d	W8 D57 ±3d	W12 D85 ±3d	W16 D113 ±3d	W20 D141 ±3d	W24 D169 ±3d	W28 D197 ±3d	W32 D225 ±3d	W36 D253 ±3d	W40 D281 ±3d	W44 D309 ±3d	W48 D337 ±3d	W52 D365 ±3d	28-D FU ±3d	The final study visit (for noncontinuing subjects) will occur 28d±3d after the visit at W52

**Table 3: Procedures and Assessments in Part B of IM011073 (52-Week Blinded Treatment Period)**

[figure not shown]
Visit Number	B1	B2	B3	B4	B5	B6	B7	B8	B9	B10	B11	B12	B13	B14/ EOT a	B15 a	Notes
Study Week/Day	D1	W4 D29 ±3d	W8 D57 ±3d	W12 D85 ±3d	W16 D113 ±3d	W20 D141 ±3d	W24 D169 ±3d	W28 D197 ±3d	W32 D225 ±3d	W36 D253 ±3d	W40 D281 ±3d	W44 D309 ±3d	W48 D337 ±3d	W52 D365 ±3d	28-D FU ±3d	The final study visit (for noncontinuing subjects) will occur 28d±3d after the visit at W52
Optional Renal biopsy														X		Within 2 weeks after completion of 52 weeks of study treatment or ET, if ET occurs after Week 2
Clinical drug supplies																
Randomization	X															Subjects who meet all randomization criteria
MMF issued	X	X	X	X	X	X	X	X	X	X	X	X	X	X d		All subjects
MMF administration	X-----X															All subjects

[figure not shown]
**Table 3: Procedures and Assessments in Part B of IM011073 (52-Week Blinded Treatment Period)**

[figure not shown]
Visit Number	B1	B2	B3	B4	B5	B6	B7	B8	B9	B10	B11	B12	B13	B14/ EOT a	B15 a	Notes
Study Week/Day	D1	W4 D29 ±3d	W8 D57 ±3d	W12 D85 ±3d	W16 D113 ±3d	W20 D141 ±3d	W24 D169 ±3d	W28 D197 ±3d	W32 D225 ±3d	W36 D253 ±3d	W40 D281 ±3d	W44 D309 ±3d	W48 D337 ±3d	W52 D365 ±3d	28-D FU ±3d	The final study visit (for noncontinuing subjects) will occur 28d±3d after the visit at W52
MMF accountability	X	X	X	X	X	X	X	X	X	X	X	X	X	X	X	All subjects
Blinded study treatment issued	X	X	X	X	X	X	X	X	X	X	X	X	X	X d		Randomized subjects only
Blinded study treatment administration	X-----X														Randomized subjects only	
Blinded study treatment accountability		X	X	X	X	X	X	X	X	X	X	X	X	X		Randomized subjects only
Unused blinded study treatment collected		X	X	X	X	X	X	X	X	X	X	X	X	X		Randomized subjects only

aCl = anticardiolipin antibody; AE = adverse event; ANA = antinuclear antibody; APA = antiphospholipid antibody; β2GPI = beta-2 glycoprotein 1; BP = blood pressure; C = complement; D = day; ECG = electrocardiogram; EOT = end of treatment; ET = early termination; FU = follow-up (end-of-study visit); HR = heart rate; hsCRP = high-sensitivity C-reactive protein; Ig = immunoglobulin; IGRA = interferon-gamma release assay; IP = investigational product; IRT = interactive response technology; LA = lupus anticoagulant; MPA = mycophenolate mofetil; MPA = mycophenolic acid; OSS = Ohio SLE Study; rSEI = revised Safety of Estrogens in Lupus Erythematosus National Assessment (SELENA) Flare Index; SAE = serious adverse event; TB = tuberculosis; UA = urinalysis; UPCR = urine protein:creatinine ratio; US = United States; W = week; WOCBP = women of childbearing potential

a Visit B14 is the last treatment visit for subjects who do not continue treatment during the LTE Period. Only these noncontinuing subjects should attend Visit B15.  
b Subjects should be instructed to not take pain medication for 12 hours before all study visits in Part B except for the 28-day follow-up visit (Visit B15).  
c If the difference in UPCR values between the two 24-hour urine collections for Visits B7 and B14 is > 20%, a third 24-hour urine will be collected to determine the average; this third sample should be collected as soon as possible but no more than 10 days after the first two results are reported.  
d Only subjects continuing to the LTE Period will be issued MMF and blinded study treatment at the Week 52 visit for Week 52 through Week 56.  
 Note: Unless they withdraw consent for follow-up, randomized subjects who discontinue the IP early will remain in the study for follow-up purposes including Visit B15; these subjects will be assessed on a case-by-case basis regarding the optional end-of-study renal biopsy.  
 Note: For premenopausal women, study visits and 24-hour urine collections should be scheduled, when possible, for when they are not menstruating.

[figure not shown]

[figure not shown]
